### **9.2.7.2 PD-L1 Testing**

Archival (or fresh) formalin-fixed, paraffin-embedded tumor tissue must be sent to a third party laboratory for determination of PD-L1 status using the analytically validated IHC assay. Either a tissue block or a minimum of 10 unstained tumor tissue sections are acceptable. Submission of fewer than 10 unstained slides may be acceptable in some circumstances following discussion with the Medical Monitor.

An associated pathology report must be submitted with each tumor tissue specimen.

PD-L1 stained tissue samples will be assessed by a pathologist at a central laboratory identified by the Sponsor and scored as PD-L1 expressing if membrane staining is observed in  $\geq 1\%$  tumor cells among a minimum of 100 evaluable tumor cells.

PD-L1 results will be available prior to enrollment for Phase 2 subjects with non-squamous NSCLC.

### **9.3 End of Treatment**

End-of-Treatment (EOT) evaluations should be performed within 2 weeks after last dosing visit or of the decision to discontinue IMP. The EOT visit should be performed before the start of new anti-cancer therapy.

### **9.4 Post-treatment Follow-up Period**

The first follow-up visit will be 30 days ( $\pm 5$  days) after the last dose of IMP. The second follow-up visit will be 100-110 days after the last dose of IMP. Adverse events and SAEs with onset up to 100 days after the last dose of IMP should be reported, as should any SAEs that occur after that time and are considered potentially related to IMPs or study procedures. Subjects will be contacted at least every 100 days after the last dose for survival follow up and recording of new anti-cancer therapies. All new treatments for cancer should be recorded, including nivolumab if received after discontinuation from this study. Subjects who complete or discontinue treatment without progression will have tumor assessments collected until a new anti-cancer therapy is started, unequivocal disease progression is documented, withdrawal of consent for follow-up contacts, or death.

### **9.5 Study Procedures for Subjects Ongoing at the Time of Data Cutoff for Completion of Analyses and Preparation of CSR**

For subjects who are continuing to receive study treatment at the time of data cutoff for completion of analyses and preparation of the CSR, the Sponsor will continue to supply study

drug (mogamulizumab and nivolumab) until the subject has completed the maximum treatment period of 96 weeks from Cycle 1 Day 1 (Section 6.3) or until the subject meets one of the criteria for removal from therapy as described in Section 7.5.

Procedures to be followed for all ongoing subjects, i.e., subjects who are continuing to receive study treatment or who are in safety or survival follow-up, at the time of data cutoff are described below. These procedures should be implemented upon notification by the Sponsor and approval by the appropriate IRB.

#### Study Drug Administration (Subjects Actively Receiving Study Treatment)

Study treatment should continue to be administered according to the protocol (as specified in Section 8.1) and the Pharmacy Manual until a maximum treatment period of 96 weeks from Cycle 1 Day 1 (Section 6.3) or until any of the criteria for removal of subjects from therapy are met (as defined in Section 7.5).

#### Efficacy and Safety Assessments

Investigators should follow study subjects in accordance with the standard of care at their Institution with respect to assessments of disease status and safety/tolerability, including the use of local clinical laboratories. There will be no further central laboratory requirements.

Blood samples for pharmacokinetic (PK), pharmacodynamic (PD) and anti-drug antibody (ADA) analyses will no longer be collected.

Survival follow-up contacts and procedures will be discontinued for all subjects.

#### Data Collection

Data entry in the electronic data capture system, defined as the clinical database, will be terminated for all subjects and all data (including SAEs and treatment-related AEs), upon written notification by the Sponsor.

Required data collection will be limited to SAEs and treatment-related AEs, which will be reported only to the KKD Drug Safety Surveillance Department using the SAE form (see Section 10.3.2.2.1).

## **10 EFFICACY, PHARMACOKINETIC, SAFETY, AND OTHER VARIABLES**

### **10.1 Study Endpoints**

#### **Primary Endpoints:**

- Safety and tolerability will be evaluated by assessing AEs, and changes in physical examination findings, vital sign measurements, 12-lead ECG readings, and clinical laboratory evaluations.

#### **Secondary Endpoints:**

- Best overall response (BOR) evaluated using RECIST v. 1.1. BOR is defined as the best response designation recorded between the date of first dose of IMP and the date of subsequent anti-cancer therapy (excluding on-treatment palliative radiotherapy of non-target bone or CNS lesions). Note: Continuation of nivolumab after discontinuing combination therapy does not count as start of new therapy for this definition. A BOR of CR or partial response (PR) requires confirmation of the assessment at least 4 weeks later.
- Time to response (TTR): Days from Cycle 1 Day 1 through the first assessment date of confirmed CR/PR using RECIST v. 1.1;
- Duration of response (DOR): Days from the first assessment date of confirmed CR/PR through the date of death or PD, whichever is earlier using RECIST v. 1.1;
- Progression-free survival (PFS): Days from Cycle 1 Day 1 through the date of death or PD, whichever is earlier. For subjects whose BOR is PR or CR using RECIST v. 1.1, the date of first documentation of objective tumor progression or death which occurs after the last documentation of PR or CR will be used as the event date for PFS;
- Overall survival (OS): Days from Cycle 1 Day 1 until the date of death.

#### **Exploratory Endpoints:**

- Pharmacokinetic parameters:
  - Mogamulizumab: observed minimum serum concentration at the end of a dosing interval ( $C_{min}$ ) and  $C_{max}$ ; and
  - Nivolumab:  $C_{min}$ .
- Immunogenicity: Anti-mogamulizumab antibody and anti-nivolumab antibody;
- Pharmacodynamic parameters: biomarkers may include, but are not limited to, immune cell subsets and factors such as cytokines and chemokines in tumor and/or blood.
- Immune-related overall response rate and DOR evaluated using irRECIST.

### **10.2 Pharmacokinetic, Pharmacodynamic, and Immunogenicity Assessments**

Blood sample collection for serum concentrations (PK), PD markers, and ADA will occur at baseline and at selected times during the treatment and post-treatment periods ([Table 10.2-1](#)).

Immunogenicity samples will be analyzed for anti-nivolumab antibodies by a validated immunogenicity assay; samples may also be analyzed for neutralizing antibodies by a validated method. Serum samples may be analyzed by an exploratory method that measures anti-drug antibodies for technology exploration purposes; exploratory results will not be reported.

Details of the collection, storage, and shipment of samples are described in the Laboratory Manual.

As of Amendment 3, blood samples for PK, PD and ADA analyses will no longer be collected.

**Table 10.2-1 Pharmacokinetic, Pharmacodynamic, and Immunogenicity Blood Sampling Schedule**

Sampling Timepoint g		PK Sampling		ADA Sampling	PD Sampling a
Cycle	Day (Visit Window)	Pre-dose b	End of Mogamulizumab Infusion c	Pre-dose	Pre-dose
1	1	X	X	X d	X
	15 ( $\pm 2$ )	X	X	-	X
2	1	X	X	X d	X
	15 ( $\pm 3$ )	X	X	-	X
3	1	X	X	X f	X
4	1	X	X	X d	X
8	1	X	X	X d	
12	1	X	X	X d	X e
Sampling Timepoint g		PK Sampling		ADA Sampling	PD Sampling
During an Infusion-related Reaction		X	X	X d	X e
Post Last Dose of IMPs-Follow Up	Day 100-110	X	X	X d	X

a: Sampling for immune cell subset analyses by FCM pre-dose Cycles 1 to 4 and Cycles 1 and 2, Day 15. Other exploratory biomarkers including PGx analysis (pre- and post-treatment) will be considered for future analysis.

b: PK Sampling at this timepoint for both nivolumab and mogamulizumab.

c: Within 15 minutes after EOI. Collect from the arm contralateral to where the relevant IMP was administered.

d: ADA sampling at this timepoint for both nivolumab and mogamulizumab.

e: Only samples for cytokine assay will be drawn at this time point.

f: ADA sampling at this timepoint only for mogamulizumab.

g: For subjects who are ongoing, i.e., subjects who are continuing to receive study treatment or who are in safety or survival follow-up, at the time of data cutoff for completion of analyses, blood samples for PK, PD and ADA analyses will no longer be collected (see Section 9.5).

ADA=anti-drug antibody; EOI=end of infusion; FCM=flow cytometry; IMP=investigational medicinal product;

PD=pharmacodynamic; PGx=pharmacogenomics; PK=pharmacokinetic.

### 10.3 Safety Assessments

Adverse events; clinical laboratory tests (serum chemistry, thyroid function testing, hematology, coagulation profile, and urinalysis); immunogenicity; vital signs; 12-lead ECGs; and physical examination (including body weight, etc.) will be evaluated to determine the safety profile in this combination regimen.

(See Section 9.5 for reporting requirements/procedures for subjects who are ongoing in the study, i.e., subjects who are continuing to receive study treatment or who are in safety or survival follow-up, at the time of data cutoff for completion of analyses.)

### **10.3.1 Definitions**

#### **10.3.1.1 Adverse Events**

An AE is defined as any untoward medical occurrence in a patient or clinical investigation subject administered a pharmaceutical product and which does not necessarily have a causal relationship with the treatment. An AE can therefore be any unfavorable and unintended sign (including an abnormal laboratory finding, for example), symptom or disease temporally associated with the use of an IMP (or biologic) whether or not considered related to the IMP.

An AE includes but is not limited to:

- Any clinically significant worsening of a pre-existing condition;
- An AE occurring from overdose of an IMP;
- An AE occurring from abuse (e.g., use for non-clinical reasons) of an investigational or marketed product.

The Investigator will inquire about AEs at all subject visits by asking the subject a non-leading question such as: "How have you been feeling since your last visit?" All AEs, whether observed by the Investigator or reported by the subject, must be collected. The collection of AE and SAE information commences following the subject's written consent to participate in the study. If a subject experiences an AE or SAE, the subject will receive appropriate treatment and supportive care as necessary, and the Investigator will continue to follow up until there is a return to the subject's baseline condition, or until a clinically satisfactory resolution is achieved.

Clinical laboratory abnormalities that qualify as AEs (other than those meeting the definition for serious) and any events that lead to an intervention (including premature discontinuation of IMP or additional concomitant therapy), other than those reported as SAEs, will be reported and evaluated as AEs. Any clinically important changes noted during interim or final physical examinations, 12-lead ECGs, x-rays, or any other potential safety assessments, whether or not these procedures are required by the protocol, must also be recorded.

For this study, disease progression should **not be** reported as an AE. Lymphopenia and leukopenia are expected pharmacologic effects of mogamulizumab and should also **not be** reported as an AE for this study. Lymphocytes and white blood cell counts will be monitored and evaluated with the laboratory data.

#### **10.3.1.2 Serious Adverse Events**

An SAE is defined as any AE that:

- Results in death;

- Is immediately life-threatening;
  - The term “life-threatening” as part of the definition of “serious” refers to an event in which the subject was at risk of immediate death at the time of the event; it does not refer to an event that hypothetically might have caused death if it were more severe;
  - If an event is Grade 4 by CTCAE v. 4.03, it does not necessarily meet the definition for life-threatening as is required for expedited regulatory reporting of SAEs.
- Requires inpatient hospitalization or prolongation of existing hospitalization.
  - Hospitalizations for pre-planned procedures are not considered SAEs.
- Results in persistent or significant disability or incapacity or substantial disruption of the ability to conduct normal life functions;
- Is a congenital anomaly or birth defect;
- Is another important medical event. Important medical events are those that may not result in death, be life-threatening, or require hospitalization, but may be considered an SAE when, based upon appropriate medical judgment, they may jeopardize the subject and may require medical intervention to prevent one of the outcomes listed above.
  - Examples of such medical events include allergic bronchospasm requiring intensive treatment in an emergency room or at home, or blood dyscrasias that do not result in inpatient hospitalization, or the development of drug dependency or drug abuse.

The term “severe” is often used to describe the intensity (severity) of a specific event (as in mild, moderate, or severe myocardial infarction); the event itself, however, may be of relatively minor medical significance (such as severe headache). This is not the same as “serious,” which is a regulatory definition as outlined above. Seriousness (not severity) serves as a guide for defining regulatory reporting obligations.

#### **10.3.1.3 Causality**

The causal relationship of each AE to the trial medication must be determined by a medically qualified individual. The causal relationship should be assessed as one of the following:

**Table 10.3.1-1 Relationship of Adverse Events**

Related:	There is a reasonable causal relationship between the study drug administration and the AE
Not related:	There is not a reasonable causal relationship between study drug administration and the AE

The term “reasonable causal relationship” means there is evidence to suggest a causal relationship  
AE=adverse event.

#### **10.3.1.4 Severity**

The severity of AEs will be graded using CTCAE v. 4.03. If a subject is responding to an ongoing steroid taper and no other intervention is required, the steroid taper should not be

considered an intervention for the purpose of CTCAE grading of AEs that have otherwise resolved to  $\leq$  Grade 1.

### **10.3.2 Adverse Event Reporting**

#### **10.3.2.1 Reporting Period**

The collection of AE information begins following the subject's written consent to participate in the study. For screen failures, SAEs should be collected and recorded only until the subject fails screening or withdraws consent to participate in the study, except for SAEs that occur outside of that window which are attributed to screening-specific procedures. All AEs with onset after signing of the ICF should be collected. Adverse events which occur prior to first administration of IMP should be identified as occurring pretreatment. No AE data should be entered on the electronic Case Report Form (eCRF) for screen failures. All AEs and SAEs with onset up to 100 days after the last dose of IMP should be reported. The Investigator should report any SAE that occurs after this period if the SAE is believed to be related to IMP or to a protocol-specific procedure. (NOTE: Upon implementation of Amendment 3, any treatment-related AEs and SAEs with onset after the last dose of IMP should be reported at the discretion of the Investigator to KKD Drug Safety Surveillance Department using the SAE form (Section [10.3.2.2.1](#)).

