#### **10.3.2.2.1 Serious Adverse Event Reporting Instructions**

Serious adverse events require expeditious handling to comply with regulatory requirements. Any SAE occurring in a clinical study subject and follow-up SAE documentation must be reported to the Sponsor's Drug Safety Surveillance Department or designee within 24 hours of the Investigator having knowledge of the SAE.

The Investigator or other qualified individual at the investigative site must complete the SAE form and fax or e-mail it to the Sponsor or designee. **All telephone communication regarding an SAE must be followed by a written report.**

The Investigator is obligated to immediately report to the Sponsor or designee any SAE occurring at any time during the reporting period (Section 10.3.2.1), independent of the circumstances or suspected cause. In addition, the Investigator must promptly report to the Sponsor any SAE occurring at any other time after completion of the study if a causal relationship to IMP is suspected. For all SAEs, the Investigator is obligated to pursue and provide information as requested by the Sponsor in addition to that requested on the SAE form. Information must include a description of the AE in sufficient detail to allow for a complete medical assessment of the case and independent determination of causality. Supporting documentation such as hospital discharge summaries or pertinent laboratory reports should also be sent to the Sponsor. In the case of a subject death, a summary of available autopsy findings must be submitted as soon as possible to the Sponsor. The Investigator will ensure that information reported immediately by telephone or other means and information entered on the SAE form is accurate and consistent.

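### After Amendment 3, Section 10.3.2.1 leaves reporting of post-dose serious events to the investigator, while Sections 9.5 and 10.3.2.2.1 make it mandatory

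*Protocol*

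**What the plan says.** Section 10.3.2.1 of the protocol starts from a firm rule: "All AEs and SAEs with onset up to 100 days after the last dose of IMP should be reported". Its next sentence extends this beyond day 100: "The Investigator should report any SAE that occurs after this period if the SAE is believed to be related to IMP", and adds SAEs attributed to a protocol procedure. A note for the period after Amendment 3 then follows: "any treatment-related AEs and SAEs with onset after the last dose of IMP should be reported at the discretion of the Investigator". The note names the SAE form to Drug Safety as the route and refers the reader to Section 10.3.2.2.1.

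Three other places bear on the same events.

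- **Section 9.5**, also written for the period after data cutoff, sets procedures for "all ongoing subjects, i.e., subjects who are continuing to receive study treatment or who are in safety or survival follow-up". Under its Data Collection heading it says: "Required data collection will be limited to SAEs and treatment-related AEs, which will be reported only to the KKD Drug Safety Surveillance Department". It contains no discretion clause and no restriction to events that start during treatment.
- **Section 10.3.2.2.1** opens with a mandatory 24-hour report for any SAE in a study subject. It goes on: "The Investigator is obligated to immediately report to the Sponsor or designee any SAE occurring at any time during the reporting period", whatever the suspected cause. It then requires prompt reporting of an SAE after study completion if IMP is suspected.
- **Section 9.4** repeats the general rule, "Adverse events and SAEs with onset up to 100 days after the last dose of IMP should be reported", without mentioning Amendment 3.

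**The concern.** One sentence in the current protocol makes optional what two other sections make compulsory. A site reading only the note could reasonably conclude that an SAE starting after the final infusion need not be reported.

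The timing makes this more important. After Amendment 3, EDC entry closes on the sponsor's notice, and central laboratory work, PK, PD and ADA sampling, and survival contacts all stop. The SAE form is then the only data route that Section 9.5 still requires. Meanwhile subjects may go on being dosed up to 96 weeks from Cycle 1 Day 1. Section 8.5.3 gives nivolumab a half-life of up to 25 days, so the 100-day window spans 100/25 = 4 such half-lives, and events early in it arise while drug is still present.

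**Working it through.** The plan states no figure on this point and no arithmetic decides it. The check is whether the passages can be followed together.

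**1. Does the conflict depend on how the note is parsed?** The word treatment-related can be read in two ways.

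| Reading of the note | What becomes discretionary | What it contradicts |
|---|---|---|
| It qualifies AEs only | Related AEs and every SAE starting after the last dose | Section 9.5 (both types required); Section 10.3.2.2.1 (24-hour rule for any SAE) |
| It qualifies AEs and SAEs | Related AEs and related SAEs | Section 9.5; the 24-hour rule; the duty in 10.3.2.2.1 to report suspected-related SAEs even after study completion; the sentence just before the note in 10.3.2.1 |

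Under the second reading the note says nothing about unrelated SAEs. Discretion would then apply to the related events but not to the unrelated ones, which is hard to see as intended. The conflict stands either way.

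**2. Can Section 9.5 be confined to events that start on treatment?** Its scope includes subjects already in safety or survival follow-up. Re-treatment is no longer allowed after Amendment 3 (Section 8.1.6), so any new event in those subjects starts after their last dose. If Section 9.5 covered only on-treatment onset, it would require no new events at all from subjects whom it expressly includes.

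**3. Does the note reach only late follow-up?** No. From Cycle 2 both drugs are given on Days 1 and 15 (Table 8.1.1-1). Section 8.1.4 generally ends treatment permanently after a related event that meets the DLT criteria. If such an event starts between two infusions and no further dose is given, its onset falls after the last dose. The note therefore also covers toxicities that end treatment in subjects who were on drug when the amendment took effect.

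**4. Which sentences in 10.3.2.2.1 stand independently of the note?** The sentence about the reporting period takes its period from Section 10.3.2.1, so it could be read as following the note. The 24-hour sentence and the post-completion sentence have no such link. The contradiction rests on those two and on Section 9.5.

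**The case against.** The strongest reply is that the amendment meant to reduce post-treatment reporting. The Summary of Changes ties continued SAE and related-AE reporting to subjects still on treatment when the amendment is implemented. On that view Section 9.5 fixes the type of data and the route, and Section 10.3.2.1 fixes the time window. This is arguable as evidence of intent, but the operative text of Section 9.5 includes subjects in follow-up, and step 3 of the working arises even among those still on treatment.

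Two further parts of the reply are sound. Section 9.4 is not a separate contradiction, because Sections 7.5, 9 and 10.3 and the footnote to Table 9-2 send ongoing subjects to Section 9.5. The reporting-period sentence in 10.3.2.2.1 is also weak support, for the reason given in step 4.

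A reader might infer that a site could lawfully leave a post-dose SAE unreported, or that the note removes the last safeguard. The documents do not support either inference. The independent duties in Section 10.3.2.2.1 remain, and Section 13.2.6 binds the investigator to GCP and the applicable regulations. What the text shows is conflicting instructions. Under-reporting is a reasonable inference from them and is not stated anywhere.

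**Conclusion.** The concern holds as an inconsistency within the current protocol. A site that follows the Amendment 3 note can fail to report serious events that Sections 9.5 and 10.3.2.2.1 require. It should be corrected.

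It affects subjects on treatment or in follow-up at data cutoff. Their number is not given, so no expected count of missed events can be worked out.

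Because safety is the primary objective, a reader might also infer that the primary safety analysis is at risk. The documents do not support that. Section 4.13.1 of the SAP does count treatment-emergent events to 100 days after the last dose. However, the note operates once EDC entry is closing, and the later events go only to Drug Safety. The effect on the SAP tables is therefore probably small. This assumes that the tables are built from the EDC database as it stands when entry ends.

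**What to change.** Delete the discretion phrase from the Amendment 3 note altogether, and state one rule in its place:

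- SAEs and treatment-related AEs that start within 100 days of the last dose go to Drug Safety on the SAE form.
- Any later SAE suspected to be related to IMP goes by the same route. The existing sentence on procedure-related SAEs stays as it is.

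Removing the discretion only within the 100 days would not be enough. Related SAEs after day 100 would stay optional, against both Section 10.3.2.2.1 and the sentence that precedes the note.

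Section 9.4 also needs a line. It asks for all AEs to day 100, whereas Section 9.5 asks only for SAEs and related AEs, so the note cannot agree with both. Section 9.4 should say that after Amendment 3 Section 9.5 governs ongoing subjects, and that unrelated non-serious AEs are no longer collected for them.

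The cost is a short edit to two sections and a few more SAE forms. The analysis does not change.
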